### 3.1.3 Reinduction

- Patients with stable disease for 3 months' duration after completion of ipilimumab therapy (usually week 12) will be offered re-induction ipilimumab at 3 mg/kg at the treating physicians discretion.
- Patients with a confirmed partial or complete response after completion of ipilimumab therapy (usually week 12) will be offered re-induction ipilimumab at 3 mg/kg at the treating physicians discretion.

### 3.1.4 Follow-up

- Subjects who are no longer receiving ipilimumab because of unacceptable toxicity (refractory Grade > 3 immune-mediated adverse reactions) or due to investigator judgment are managed in follow-up. Efficacy assessments for these subjects during follow-up are as per the standard of care. Date of death is recorded.
- Subjects who discontinue ipilimumab treatments should be followed until death or the closure of the study (whichever is first).
- Subjects who are no longer receiving ipilimumab because of clinical progression and who have switched to alternative treatment are not followed formally except to record the date of death.

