## **5.4 Discontinuation of Study Therapy**

Subjects **MUST** be discontinued from study therapy AND withdrawn from the study for the following reasons:

Withdrawal of informed consent (subject's decision to withdraw for any reason)

Any clinical adverse event, laboratory abnormality or intercurrent illness which, in the opinion of the investigator, indicates that continued treatment with study therapy is not in the best interest of the subject

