## **6.10 Definition of Efficacy Assessments**

- Rate of progression-free survival of ipilimumab and SABR in patients with oligometastatic melanoma as measured from the time of study enrollment until the first documented date of disease progression by both mWHO and irRC criteria.
- Frequency of grade 3 and grade 4 toxicities according to CTCAE (Common Toxicity Criteria for Adverse Events) version 4
- Frequency of objective response rate, defined as complete response + partial response, measured by mWHO criteria based on radiographic response rate will be determined based on re-staging CT of the chest, abdomen and pelvis
- Frequency of objective response rate, defined using the immune related response criteria (irRC) based on radiographic response rate will be determined based on re-staging CT of the chest, abdomen and pelvis
- Rate of local failure, as measured from the time of study enrollment until the first documented date of failure within the irradiated field
- Rate of overall survival, as measured from the time of study enrollment until the time of death

Biopsy, clinical evidence and radiographic evidence are all acceptable and will be used to document progression.

Overall survival: will be calculated as the time from entry on the study until the time of death.

Re-staging imaging with contrast-enhanced CT or MRI of the chest, abdomen, and pelvis will be performed before treatment, prior to 3rd ipilimumab infusion, 4 weeks after the final ipilimumab infusion (week 14 if there are no interruptions), and every 3 months for the first 2 years, then every 6 months during years 2-5.

The first re-staging scans after the week 14 imaging will be done at the 6 months from enrollment time point so that the endpoint of 6 month progression-free survival can be assessed.

All patients that have been treated on protocol with SABR and ipilimumab will have re-staging imaging even if they were taken off of protocol for adverse events after the SABR. Patients who do not have SABR due to adverse events from the first 2 infusions of ipilimumab are not required to complete re-staging imaging.

Patients who meet the criteria for Complete Response or Partial Response will have a re-imaging 4-weeks later to confirm the response.

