## 7.0 STATISTICAL PLAN

### 7.1 Sample Size Determination

Overall, this study will require 32 evaluable patients. We estimate that we will accrue 1-2 patients per month; therefore, thus, the minimum study duration will be 16 months (2 accruals per month) and the maximum is 32 months (1 accrual per month for 32 patients).

Current literature and experience with ipilimumab in metastatic melanoma in this patient population shows that we can expect ipilimumab + SABR will not be considered promising in this patient population if at most 15% of patients are progression-free and alive at 6 months, because that is the expected 6 month PFS for ipilimumab alone. For this agent to be considered promising in this patient population, we would expect an improvement in the 6-month PFS rate to at least 35% with this regimen in this patient population. Constraining the Type I and II error rates to 10% each, the study design will require 32 evaluable patients to test these hypotheses regarding the 6-month PFS rate with ipilimumab when given in combination with the stereotactic ablative radiation therapy in this patient population. If we see at least 8 patients who have are alive and progression-free at 6 months after initiation of treatment out of the 32 evaluable patients, we will consider this sufficient evidence that this regimen has promising activity in this patient population. Otherwise, if 7 or fewer patients have are alive and progression-free at 6 months, we will consider this regimen to not be sufficiently active in this population of oligometastatic melanoma patients.

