## Appendix II: Study Schedule

	Pre-Treatment		During Treatment						Follow-Up visits start within 30 days of last dose (+/- 20 days), with the goal of 30 days for the first follow-up visit.			
	≤ 4 Week prior to first treatment	≤3 days Prior To first treatment	Day 1	Prior to Week 4	Week 5 Before SABR	Prior to Week 7	Prior to Week 10	Week 14	Q3 months for first 2 years	Q6 months for year 2- 5	Annually for 5 years	At Progression
History and physical exam	X			X				X	X	X	X	
Consent Obtained	X											
Record Prev. Therapies	X											
Blood Specimen Banking			X	X	X	X	X	^	\$			
Vital signs	X		X	X		X	X	X	X	X	X	
EKG	X											
Diagnostic biopsy	*											*
Contrast-enhanced CT or MRI of the abdomen and pelvis	X					X @		X @	*	*	*	
CT chest	X					X		X	*	*	*	
Whole-body PET-CT scan of body (optional)	X								*	*	*	
CBC w/diff & ANC, platelets	X		X	X		X	X	X	X	X	X	
CMP including LFTs	X		X	X		X	X	X	X	X	X	
Thyroid Fxn and ACTH level	X			X		X	X	X	X	X	X	
CrCl assessment	X											
Urinalysis	X											
Continue to next page												

	≤4 weeks prior to first treatment	≤3 days Prior To first treatment	Day 1	Prior to Week 4		Prior to Week 7	Prior to Week 10	Week 14	Q3 months for first 2 years	Q6 months for year 2- 5	Annually for 5 years	At Progression
Serum pregnancy test	X	x x										
HIV, Hep B and C test	X											
Ipilimumab			X	X		X	X					
SABR						X						
Adverse event evaluation			X	X		X	X	X	At 90 xx days post-treatment			
Tumor banking	*											*

\*preferred/at the discretion of the treating physicians

xxmandatory

^ Post-treatment blood draw will occur at week 12 (two weeks after 4th ipilimumab infusion)

\$ During the follow-up period blood collections will occur at week 16, week 20, week 24, week 35 and week 50 per Section 3.4.

@ Will delayed if ipilimumab dosing is delayed: CT will be prior to infusion 3, and 4 weeks after infusion 4.

xx SAEs are to be reported to sponsor and IRB up to 70 days after last treatment with ipilimumab per protocol

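### The 6-month scan that decides the primary endpoint is required in one section and optional in others, and no missing-scan rule is stated, so the design's 91.8% power is not protected

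*Combined protocol and SAP*

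**What the plan says.** **Imaging required.** Section 6.10 places the first re-staging after week 14 at 6 months from enrollment, expressly so that the primary endpoint can be assessed. Patients treated with both SABR and ipilimumab "will have re-staging imaging even if they were taken off of protocol for adverse events after the SABR". Section 6.10.2 separately calls for CT every 3 months after the on-study period.

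**Imaging optional or in doubt.**
- Section 3.1.4, for patients off ipilimumab because of unacceptable toxicity or investigator judgment: "Efficacy assessments for these subjects during follow-up are as per the standard of care". Its next bullet has patients who discontinue followed until death or study closure, but does not say with what imaging.
- Section 5.4 says subjects must "be discontinued from study therapy AND withdrawn from the study for the following reasons". The list includes any adverse event that, in the investigator's opinion, makes further study treatment contrary to the patient's interest. Section 4.5.2, by contrast, continues protocol evaluations for a patient who leaves the intervention but agrees to follow-up.
- Appendix II requires CT before week 7 and at week 14. Every later CT cell carries an asterisk, defined as "preferred/at the discretion of the treating physicians", and there is no column for 6 months from enrollment.

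**Endpoint and design.** Section 7.1: "Overall, this study will require 32 evaluable patients". The regimen is unpromising "if at most 15% of patients are progression-free and alive at 6 months". For it to be promising, "we would expect an improvement in the 6-month PFS rate to at least 35% with this regimen in this patient population". The errors are set as follows: "Constraining the Type I and II error rates to 10% each, the study design will require 32 evaluable patients". Success is 8 or more of 32. In section 7.2 the numerator is patients alive with CR, PR or SD on re-staging imaging at 6 months; the denominator is those who received ipilimumab and SABR. Section 7.3 adds a minimum of two ipilimumab doses. Neither section sets an imaging condition for entering the denominator.

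**The concern.** The trial is decided by one count out of 32, and each patient's contribution rests largely on one scan. A site working from the calendar or from section 3.1.4 could skip that scan and still be following the protocol. Under the literal 7.2 definition, a patient who is in truth alive and progression-free but unscanned is lost from the numerator and kept in the denominator. The observed rate is then too low and the chance of recognizing an active regimen falls. Losses are also likely to concentrate in patients who stop for toxicity, whose outcomes may differ from the rest, so it would be unsafe to assume that they are random. A 6-month scan that was not done cannot be recovered at analysis.

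**Working it through.** **Inputs.** From section 7.1: n = 32, success threshold 8, p0 = 0.15, p1 = 0.35. Let m be the share of true 6-month successes who have no 6-month scan. The documents give no value for m; 0 to 20% is an assumed range.

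**1. Reproduce the design (exact binomial).**
- Type I error = P(X ≥ 8 | 32, 0.15) = 0.0958.
- Power = P(X ≥ 8 | 32, 0.35) = 0.9182.

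Both meet the stated limits, and 32 is the smallest single-stage n that does so. The Study Summary calls the design a two-stage Simon minimax, while 7.1 gives no first-stage boundary. An exact search for that design also gives n = 32 (stop if 2 or fewer of 17 succeed; reject the regimen if 7 or fewer of 32 succeed), with type I error 0.0906 and power 0.9053.

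**2. Which patients can cause a loss.** Only true successes inside the denominator matter.

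| Group | In denominator? | Can a true success be lost? |
|---|---|---|
| Off ipilimumab for toxicity or investigator judgment after SABR, not progressed | Yes | Yes: 6.10 against 3.1.4 |
| Withdrawn under 5.4 after SABR, not progressed | Yes | Yes, unless 4.5.2 follow-up is agreed and carried out |
| Completed treatment (last planned induction dose at week 10), not progressed | Yes | Yes: Appendix II makes the CT discretionary |
| Clinical progression and switched treatment (3.1.4) | Yes | No: 6.10 accepts clinical evidence of progression, so already a failure |
| No SABR because of early adverse events | No | No |

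**3. Effect if a missing scan counts as failure and is independent of outcome.** The recorded success probability becomes p(1 − m), so power(m) = P(X ≥ 8 | 32, 0.35(1 − m)), and type I error uses 0.15(1 − m).

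| m (assumed) | Expected recorded rate at p = 35% | Power | Type I error |
|---|---|---|---|
| 0 | 35.00% | 91.82% | 9.58% |
| 2% | 34.30% | 90.52% | 8.74% |
| 3% | 33.95% | 89.81% | 8.33% |
| 5% | 33.25% | 88.28% | 7.55% |
| 10% | 31.50% | 83.68% | 5.82% |
| 15% | 29.75% | 77.93% | 4.37% |
| 20% | 28.00% | 71.01% | 3.19% |

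**4. Break-even.** Power stays at or above 90% up to m = 2.7%. With 32 × 0.35 = 11.2 true successes expected, that is 11.2 × 0.027 ≈ 0.3 of a patient. For the two-stage variant the margin is about 0.8%, and power is 86.8% at m = 5% and 82.0% at 10%.

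**5. If unscanned patients were excluded instead.** Section 7.1 has no rule for fewer than 32. Keeping the threshold at 8, P(X ≥ 8 | n, 0.35) is 89.9% for n = 31, 87.6% for n = 30 and 81.8% for n = 28. Power is lost this way too.

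**The case against.** **The stated power is met.** A reader might infer from the conflict that the trial does not have the power it claims. The documents do not support that: the written rule gives 91.8%, and every shortfall above depends on an assumed m. This objection stands.

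**No passage says that a missing scan is a failure.** That is inferred from the 7.2 numerator and denominator. The 7.1 decision rule speaks of being alive and progression-free without mentioning a scan, and the time-to-event analysis in 7.2 censors at the last tumor assessment. This also stands. It means that the gap is an unstated rule, and that treating missing as failure is the literal reading, not a written one. Calling unscanned patients non-evaluable is not an obvious escape, because the bullet on overall response in 7.2 defines evaluable by eligibility, two ipilimumab doses and SABR, without imaging.

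**The background toxicity rates are not scan-loss rates.** Section 1.5.2 reports 10% stopping ipilimumab for adverse reactions and 15% with severe immune-mediated reactions. It is tempting to use these as m, but that assumes every such patient misses a scan that 6.10 requires, and some would stop before SABR and never enter the denominator. For scale only: if 10% of true successes stopped and half of them lacked the scan, m = 5% and power is 88.3%.

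**Follow-up is partly preserved.** Sections 4.5.2 and 6.10.2 and the second bullet of 3.1.4 all point toward continued follow-up, so reading 5.4 alone would exaggerate the loss. This stands in part: those provisions do not override the discretion in Appendix II or the standard-of-care wording in 3.1.4.

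**The error is conservative.** Counting missing as failure lowers type I error. That is true, but it comes at the cost of power.

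**Conclusion.** The concern holds in a conditional form. The protocol gives incompatible instructions about the scan that determines the primary endpoint, and it does not say how a missing scan is counted. Power is sound if the scans are obtained and unprotected if they are not, with a margin on average of less than one lost true success. The size of any loss rests on three assumptions: the value of m, missingness independent of outcome, and missing treated as failure. Under that handling the observed rate is biased downward. If unscanned patients were excluded, the direction of any bias would depend on how their outcomes differ, which the documents do not allow one to judge. Patients who progressed and switched treatment, and patients who never received SABR, add nothing to the problem.

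**What to change.** 1. Reconcile 3.1.4, 5.4 and Appendix II with 6.10 and 4.5.2. State that every patient in the primary-analysis population keeps protocol imaging through 6 months from enrollment unless progression is already documented or consent for follow-up is withdrawn. This separates ending study treatment from ending outcome assessment; it does not touch the criteria for stopping treatment.
2. Add a 6-month-from-enrollment entry to Appendix II with CT marked as required (X) and an allowed window around the date.
3. State in 7.2 how a patient without a 6-month scan in the window is counted, and add a sensitivity analysis under the alternative handling (failure against exclusion). If exclusion is allowed, give the decision rule for fewer than 32 patients.

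The cost is protocol and analysis-plan wording. Section 6.10 already requires these scans, so no imaging is added and the sample size need not change.

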SABR will be delivered between the second and third doses of ipilimumab (usually week 5-6 if no delays for ipilimumab toxicity) using the following suggested schedules: 18 Gy x 3 to peripheral lung, 10 Gy x 5 to central lung, 10 Gy x 5 to liver, 6 Gy x 5 to nodal stations, 12 Gy x 3 to adrenal, 24 Gy x 1 brain < 2 cm, 18 Gy x 1 brain 2-3 cm, and 15 Gy x 1 brain > 3 cm, 16-18 Gy x 1 to vertebral sites.

Duration of therapy: Patients will receive at least 12 weeks of therapy and will be observed for toxicity for 90 days after the last ipilimumab infusion. Patients will remain on study until evidence of progression by both mWHO and irRC or death. Patients in whom new lesions develop or baseline lesions grow will receive additional ipilimumab treatments to complete induction therapy.

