## **6.8 Safety Assessments**

All patients who receive at least one dose of ipilimumab will be considered evaluable for safety parameters. Additionally, any occurrence of non-SAE or SAE from time of consent forward, up to and including follow-up visits, will be reported. See Section 8: Adverse Event Reporting.

Safety will be evaluated for all treated patients using the National Cancer Institute (NCI) Common Terminology Criteria for Adverse Events (CTCAE), Version 4.0 (<http://ctep.cancer.gov>). Safety assessments will be based on medical review of adverse event reports and the results of vital sign measurements, physical examinations, and clinical laboratory tests.

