4. action taken (no action taken; study drug dosage adjusted/temporarily interrupted; study drug permanently discontinued due to this adverse event; concomitant medication taken; non-drug therapy given; hospitalization/prolonged hospitalization)
5. whether it constitutes a serious adverse event (SAE)

All adverse events should be treated appropriately. Such treatment may include changes in study drug treatment including possible interruption or discontinuation, starting or stopping concomitant treatments, changes in the frequency or nature of assessments, hospitalization, or any other medically required intervention. Once an adverse event is detected, it should be followed until its resolution, and assessment should be made at each visit (or more frequently, if necessary) of any changes in severity, the suspected relationship to the study drug, the interventions required to treat it, and the outcome.

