#### **10.3.1 Serious Adverse Events**

Following the subject’s written consent to participate in the study, all SAEs must be collected, including those thought to be associated with protocol-specified procedures. All SAEs must be collected that occur within 70 days of discontinuation of dosing of the investigational product. If applicable, SAEs must be collected that relate to any later protocol-specified procedure (eg, a follow-up skin biopsy). The investigator should notify BMS of any SAE occurring after this time period that is believed to be related to the investigational product or protocol-specified procedure.

All SAEs whether related or unrelated to the ipilimumab, must be immediately reported to BMS (by the investigator or designee) within 24 hours of becoming aware of the event. If only limited information is initially available, follow-up reports are required. The original SAE form must be kept on file at the study site.

All SAEs should be faxed or emailed to BMS at:

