#### 10.3.3 Nonserious Adverse Events

The collection of nonserious AE information should begin at initiation of investigational product. Nonserious AE information should also be collected from the start of a placebo lead-in period or other observational period intended to establish a baseline status for the subjects.

If an ongoing nonserious AE worsens in its intensity, or if its relationship to the investigational product changes, a new nonserious AE entry for the event should be completed. Nonserious AEs should be followed to resolution or stabilization, or reported as SAEs if they become serious. Follow-up is also required for nonserious AEs that cause interruption or discontinuation of investigational product, or those that are present at the end of study participation. Subjects with nonserious AEs at study completion should receive post-treatment follow-up as appropriate.

All identified nonserious AEs must be recorded and described in the medical record.

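### Section 3.1.4, read literally, ends adverse event follow-up when a patient switches treatment after clinical progression, against the protocol's own 90-day toxicity observation; the likely effect is small

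*Combined protocol and SAP*

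**What the plan says.** Three rules on follow-up after ipilimumab bear on this point.

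- **Toxicity window.** The Study Summary and sections 3.1.2 and 6.1 each state that patients "will be observed for toxicity for 90 days after the last ipilimumab infusion". The adverse event row of Appendix II has an evaluation at week 14 and another 90 days after treatment. None of these exempts patients who change therapy.
- **Follow-up after stopping.** Section 3.1.4 has three bullets. The second follows everyone who stops ipilimumab until they die or the study closes. The third concerns those who stop for clinical progression and "who have switched to alternative treatment are not followed formally except to record the date of death".
- **Event collection.** For serious events, section 10.3.1 says: "All SAEs must be collected that occur within 70 days of discontinuation of dosing of the investigational product". Later serious events are notified if believed related, and Appendix II repeats the 70-day limit. For nonserious events, section 10.3.3 gives a start, "The collection of nonserious AE information should begin at initiation of investigational product", but no end. Section 6.8 says that "any occurrence of non-SAE or SAE from time of consent forward, up to and including follow-up visits, will be reported".

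The data feed the grade 3 and 4 toxicity frequency (a secondary endpoint in section 3.3), the grade 3+ incidence in section 7.2, and possibly the safety rule in section 7.4, which stops the combination if 5 or more of 18 patients have a severe immune-related toxicity.

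**The concern.** For a patient who switches before day 90, a site cannot both observe toxicity to day 90 and drop everything except the date of death. The third bullet is the more specific rule for this group, so a site could reasonably act on it.

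Nonserious events are the exposed part. Their reporting is tied to follow-up visits, which these patients no longer formally have. Grade 3+ is not the same as serious: a grade 3 immune event managed without admission counts in section 7.2 but may never become a serious event report. Section 1.5.2 notes that hepatic immune events mostly showed as laboratory changes without symptoms, so some would not come to light unless someone asks or looks at records.

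The error has one direction. A missed event lowers the reported toxicity of the combination or leaves it unchanged. It never raises it.

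**Working it through.** The conflict is textual, so the check is which days and which events no rule clearly covers.

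**1. Timeline without delays.** Infusions at weeks 1, 4, 7 and 10 fall 0, 3, 6 and 9 weeks after the first dose. Section 6.10 puts the scan 4 weeks after the last infusion: 9 + 4 = 13 weeks after the first dose, which is calendar week 14 as the plan states, and day 28 after the last infusion. Day 90 after the last infusion is 63 + 90 = 153 days, or 153 / 7 = 21.9 weeks, after the first dose.

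**2. Scheduled evaluations.** After the last infusion, Appendix II has adverse event evaluations at week 14 and day 90. I take the 30-day visit in section 6.5.3 to be the week-14 one. A patient who switches at the week-14 scan has had the first and loses the second: 1 of 2.

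**3. Days left open for new nonserious reports.** The second row assumes a switch only after a confirmatory scan 4 weeks later (section 1.6 recommends confirmation, and Appendix III uses a 4-week gap): 28 + 28 = 56.

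| Switch (days after last infusion) | Days left to 90 | All SAEs still collected | Related SAEs only |
|---|---|---|---|
| 28 | 90 − 28 = 62 | 70 − 28 = 42 | 90 − 70 = 20 |
| 56 | 90 − 56 = 34 | 70 − 56 = 14 | 90 − 70 = 20 |

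**4. Likely number of events.** Section 1.5.2 puts the common onset of immune-related events at 3 to 10 weeks from the first dose. The week-14 scan is 13 − 10 = 3 weeks past that window. That experience is with ipilimumab, not with the combination. An earlier switch would fall inside the window, but section 3.1.2 recommends all four doses while performance status is stable.

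**5. Reach into section 7.4.** The rule stops at a count of 5 or more, so one missed patient changes stop to continue only if the true count is exactly 5. With X ~ Bin(18, q), P(X = 5) = 8568 × q⁵ × (1 − q)¹³:

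- q = 0.30: 8568 × 0.00243 × 0.00969 = 0.20
- q = 0.15: 8568 × 0.0000759 × 0.1209 = 0.08

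The missed event must also occur before the look and be the patient's only qualifying event.

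**6. Illustration with assumed inputs.** The documents give no share of missed events. Suppose 20–60% of patients switch in the window, 5–20% of severe immune events start after the switch, and 25–50% of those are nonserious. The missed share m then runs from 0.20 × 0.05 × 0.25 = 0.0025 to 0.60 × 0.20 × 0.50 = 0.06. With q = 0.30 × (1 − m), P(X ≥ 5) falls from 0.667 with nothing missed to between 0.665 and 0.604. This leans towards overstating the effect, because it treats every missed event as due before the look and as the patient's only one.

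**The case against.** The strongest reply is that the texts can be read together. Sections 3.1.2 and 6.1 state toxicity observation separately from staying on study until progression, so progression need not end it. Section 3.1.4 is mainly about efficacy follow-up and survival, and its third bullet might end only the former. This reading is possible but strained, because the bullet removes formal follow-up with a single exception, the date of death. If the sponsor meant the milder reading, the amendment merely says so.

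The second reply is that other rules shrink the gap, and this largely stands. Section 10.1.1 counts important medical events as serious, and section 10.3.1 asks for a serious event report where seriousness is in doubt. Severe enterocolitis and grade 3–5 hepatotoxicity call for systemic steroids (section 5.5), so many would arguably qualify without admission. Section 6.6.1 documents new and continuing events at early withdrawal, section 10.3.3 follows nonserious events still present when participation ends, and section 6.9 adds: "Once an adverse event is detected, it should be followed until its resolution". None of these captures a new, clearly nonserious grade 3+ event that begins after the switch.

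A reader might go further in four ways that the documents do not support:

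- **Serious events are lost.** They are not; section 10.3.1 covers them independently of follow-up visits.
- **Nine weeks of active surveillance disappear.** Appendix II schedules nothing for adverse events between week 14 and day 90 for any patient. One evaluation is lost, plus unscheduled reports.
- **The second and third bullets contradict each other on safety.** The second names no adverse event collection, and recording the date of death is one way of following a patient until death. It adds little.
- **The section 7.4 rule is compromised.** That section gives no observation window, so nothing says that events to day 90 enter the look.

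Limiting collection after a switch also has a rationale, since later therapy confuses attribution. But the plan commits to 90 days without that limit.

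**Conclusion.** The point holds as a minor inconsistency. Taken literally, the third bullet of section 3.1.4 removes a safety evaluation that the protocol requires elsewhere without exception. It matters only for patients who stop for clinical progression and switch within 90 days of the last infusion.

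The remaining loss is the day-90 evaluation, new clearly nonserious grade 3+ events after the switch, and events on days 71–90 not reported as related serious events. The number cannot be estimated from the documents. It is probably small if onset under the combination resembles the ipilimumab experience and if most patients complete four doses. The bias is one-directional for the grade 3+ incidence in sections 3.3 and 7.2. An effect on section 7.4 needs all of the following: an event before the look, in a patient with no other qualifying event, with a true count of exactly 5.

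**What to change.** Replace the third bullet of section 3.1.4 with wording such as:

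> Patients who stop ipilimumab for clinical progression and start another treatment stay under adverse event collection until 90 days after their last ipilimumab infusion. This covers nonserious grade 3+ immune-related events and the 90-day evaluation, obtained by contact with the patient or from the treating clinic's records. The start date of the new treatment and the attribution of each event are recorded. After day 90, only the date of death is recorded.

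The 70-day serious event rule can stay as it is. The fix needs no change to the boundary or timing in section 7.4, and no extra completeness count at that look; how much follow-up the 18 patients should have by then is a separate question.

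The cost is a few contacts or record requests per switching patient, with no added study visit or mandated test. The drawback is that some events will arise on later therapy and need an attribution judgement, which is why the start date of that therapy should be recorded.
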